In Aim 1B, we will validate the findings shown by [name] (PI) et al. demonstrating **no difference** in total bacterial colony counts or identification of pathogenic bacteria from the gloves of persons who either performed HH or did not perform HH prior to putting on non-sterile gloves. Although the findings from the pilot study demonstrate the safety of this alternative strategy, these findings need to be replicated across multiple facilities and varying patient care areas (e.g. pediatrics, emergency departments). Further validation of the pilot findings, as well as results of Aim 1a, will demonstrate generalizability and support guideline/policy change and implementation.

REFERENCES:

1. Centers for Disease Control and Prevention. Guideline for Hand Hygiene in Health-Care Settings: Recommendations of the Healthcare Infection Control Practices Advisory Committee and the HICPAC/SHEA/APIC/IDSA Hand Hygiene Task Force. *MMWR*. Oct 25 2002;51(RR-16):1-45.

2. WHO Guidelines on Hand Hygiene in Health Care. 2009;
http://apps.who.int/iris/bitstream/10665/44102/1/9789241597906_eng.pdf.

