1.5 Risk Benefit Ratio

The potential benefits of this study outweigh the minimal risks to participants.

2 Study Objectives, Aims and Hypothesis

Aim 1A: Perform a multicenter, cluster randomized trial to evaluate the efficacy of a direct gloving strategy to improve compliance with infection prevention practices (i.e. HH and glove use).

Hypothesis: When compared to the standard practice of performing HH and then donning gloves, directly gloving when gloves are indicated will increase compliance with HH and glove use.

Aim 1B: Perform a nested multicenter validation study, where gloved hands of HCWs will be randomly sampled to determine bacterial contamination of non-sterile gloves after donning.

Hypothesis: When compared to the standard practice directly gloving when gloves are indicated will have no effect on bacterial contamination of gloves.

3 Study Design and Procedure

Aim 1A:

Study Design: We will perform a cluster-randomized trial to include 14 patient care areas (i.e. units) at the University of Maryland Medical Center (UMMC), the R Adams Cowley Shock Trauma Center (STC), University of Iowa Hospitals (UIH), and Johns Hopkins Hospital (JHH). Each unit will be randomly assigned to the intervention or usual care group. Randomization will be stratified by unit type: adult intensive care, general pediatric wards, emergency departments and inpatient hemodialysis units. One unit from each of the four types at UMMC, UIH, and JHH will be selected for study participation and will be randomized; and two units (one Adult ICU and the Trauma Resuscitation Unit (comparable to the Adult ED)) will be selected and randomized from Shock Trauma. We have specifically chosen these diverse areas to avoid any potential crossover of effect from one study unit to another as units have very different personnel with very little crossover of care.

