5.1 Recruitment

Aim 1A. Ward/units will be recruited for participation in this study. This study aims to recruit from the following unit types at the UMMC: Adult ICUs, General Pediatric Wards, Emergency Departments (ED, TRU) and Inpatient Hemodialysis units. Consideration for a unit/wards participation in this study will be reviewed with the UMMC Department of Infection Prevention and Hospital Epidemiology. In addition, decisions for participation will be made in concert with Infection Prevention AND the individual unit leadership (e.g. Medical and Nursing directors). In the baseline period (previously described), compliance with HH and gown/glove use will be collected and units with similar rates of compliance (across all three sites, U Maryland, Iowa and Hopkins) will be included as study participants and will be randomized to receive the intervention or usual care. Interactions with the participating units will include education and data collection regarding compliance with infection prevention practices.

Aim 1B. The investigators will station themselves outside the rooms of patients on Contact Precautions within the units participating in the study; these rooms will be identified by the hospital infection control signs outside the door. As HCWs approach the room with intent to enter; the investigators will introduce themselves, briefly describe the study, study procedures, and will ask HCWs if they would consent to participate. It will be made clear that participation is voluntary and that there are no repercussions for declining participation. The investigators will give verbal information about the study and have written information also available. HCWs will have gloves sampled by direct sampling by agar plate.

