The primary outcome, total bacterial colony forming units (CFUs) > 30 of gloved hands, will be compared between the two groups using a comparison of proportions. In this case a one-sided $p < 0.025$ will be statistically significant for noninferiority. We will also compute a two-sided 95% confidence interval for the relative risk of CFUs > 30 comparing direct gloving to HH + gloving, where the upper bound of the confidence interval < delta will be considered statistically significant. In this analysis, we define the non-inferiority margin, or delta, equal to 1.15. We feel (in consultation with microbiologists and HH experts) that if glove reuse (intervention) were found non-inferior to usual care by a 1.15 margin (i.e. a difference of 15%) that this would be enough to lead to change in practice. Robust empirical standard errors will be calculated using generalized estimating equations with an independence working correlation matrix to account for within-site clustering for sample proportions. A secondary analysis will compare groups using CFUs as a count outcome. We will compute a two-sided 95% confidence interval for the relative mean of CFUs on gloved hands comparing the intervention to the usual care group. The upper bound of the confidence interval < delta will be considered statistically significant, where delta is 1.15. The secondary outcomes, presence of pathogenic bacteria and total number of pathogenic and non-pathogenic bacteria present, will be analyzed like the primary outcome.

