Based on pilot data, we anticipate 5% of HCWs in the usual care group (hand-hygiene plus gloves) and 3.5% in the experimental group (direct gloving) to have > 30 CFUs. We define non-inferiority as a relative risk < 1.15 of having > 30 CFUs, comparing the experimental group to the usual care group. That is, delta equal to 1.15. Under these assumptions, 1280 samples (per group) are sufficient for a one-sided test with alpha=0.025 to have 80% power to detect noninferiority.²³ 1280 samples in both groups will result in a total of 2560 samples for the 12-month study period. Spread across the 14 proposed participating units at the 3 healthcare systems (UMMC and STC will share a Research Associate), this is approximately 850 samples per site and 180 samples per participating unit over the 12-month study period. Thus, each site will need to recruit just over 70 HCWs each month to meet the goal sample size. In the pilot study 230 HCWs were recruited and agreed to participate in a single month.

7 Data Collection, Handling and Storage

All data collected will be stored in a relational database in order to digitize the data for analysis. No PHI will be collected. The database will be stored on a shared drive. Data from University of Iowa and Johns Hopkins Hospital will be sent electronically the investigators at the University of Maryland – data from Aim 1A is aggregate unit level data and not-human subjects data; and data from Aim 1B is completely de-identified.

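### Aim 1B rests its robust standard errors on 3 or 4 sites rather than the 14 randomised units, with no small-sample method and no term for the stratification factor

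*Combined protocol and SAP*

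**What the plan says.** Section 3 (Aim 1A) sets the unit of randomisation: "Each unit will be randomly assigned to the intervention or usual care group". It adds: "Randomization will be stratified by unit type: adult intensive care, general pediatric wards, emergency departments and inpatient hemodialysis units". There are 14 units: one of each type at each of three hospitals, plus an adult ICU and a trauma resuscitation unit at the fourth. The strata therefore hold 4 ICUs, 3 pediatric wards, 4 emergency-type units and 3 dialysis units. Aim 1B is nested in these units.

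For Aim 1B, section 6.1 compares the proportion of gloved hands above 30 CFUs. It uses a one-sided 0.025 level and requires the upper 95% limit for the relative risk to lie below 1.15. The robust standard errors come from GEE "with an independence working correlation matrix to account for within-site clustering for sample proportions".

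The protocol uses the word site for a level above the unit. Section 5.1 has "across all three sites, U Maryland, Iowa and Hopkins". Section 6.2 (Aim 1B) separates the two levels in one sentence: "this is approximately 850 samples per site and 180 samples per participating unit over the 12-month study period".

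For Aim 1B the plan gives no unit-type term, small-sample correction, reference distribution, degrees of freedom, ICC or design effect. It also does not say that the one-sided p-value and the confidence limit come from the same clustered analysis.

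**The concern.** There are two separate problems.

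- **Too few clusters.** A sandwich variance is estimated from between-cluster variation. With 3 or 4 clusters it is biased downward and very unstable, and a normal critical value takes no account of either. Non-inferiority is then declared too often.
- **Stratification ignored.** Randomisation balances unit types across arms, although the two three-unit strata cannot split evenly. A model without unit type counts differences between types as noise. The actual error rate then depends on how much contamination differs between ICUs, pediatric wards, emergency departments and dialysis units. The protocol expects these areas to differ: section 3 calls them diverse, and section 1.2 says "these findings need to be replicated across multiple facilities and varying patient care areas".

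Aim 1B carries the safety claim for omitting hand hygiene before gloving. Section 6.1 says a non-inferior result would be enough to change practice, so a false non-inferiority finding is the costly error.

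**Working it through.** **Inputs from the protocol.** 14 units in strata of 4, 3, 4 and 3; 2560 samples, so 2560/14 ≈ 183 per unit; usual care 5%, direct gloving 3.5%; margin: "We define non-inferiority as a relative risk < 1.15 of having > 30 CFUs"; one-sided alpha 0.025; 80% power with 1280 per group.

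**Assumptions.** Unit-type rates (overall mean about 5%). ICC 0, 0.001 and 0.01, the last two borrowed from Aim 1A, which has a different outcome. Allocation 2 v 2 in the four-unit strata and 1 v 2 or 2 v 1 in the three-unit strata, 7 v 7 overall.

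**1. The plan's own figure.** The Farrington–Manning score formula on the risk-difference scale, with margin 0.15 × 5% = 0.0075, gives 1280 per group. It includes no design effect. The decision rule is on the relative-risk scale, where:

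- SE(log RR) = √[(0.95/0.05 + 0.965/0.035)/1280] = √(46.57/1280) = 0.191
- distance to the margin = ln(1.15/0.70) = 0.496
- power = Φ(0.496/0.191 − 1.96) = Φ(0.64) ≈ 74%, still without clustering.

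**2. Why 3 or 4 clusters inflate the error.** As a rough guide, with G equal clusters the uncorrected sandwich is too small by a factor (G−1)/G on average, and the statistic behaves like t on G−1 df multiplied by √[G/(G−1)]. For G = 3 the rule then rejects when t on 2 df is below −1.96/√1.5 = −1.60. That probability is 0.5 − 1.60/(2√(2 + 1.60²)) ≈ 12.5%, not 2.5%. Unequal sites make it somewhat worse.

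**3. Simulation of the planned rule at a true RR of 1.15.** Beta-binomial units, log-link independence GEE with arm only, uncorrected sandwich, 1.96, 20,000 trials per setting. Ranges cover the three ICC values and two sample layouts (183 per unit, or about 850 per site).

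| Assumed usual-care rates, ICU/peds/ED/dialysis | 3 sites | 4 hospitals |
|---|---|---|
| 5/5/5/5% | 13.4–13.9% | 10.5–11.5% |
| 5.0/4.2/6.0/4.5% | 11.7–13.3% | 8.6–10.5% |
| 5.0/3.7/6.7/4.0% | 8.7–12.0% | 5.7–9.1% |
| 4.9/2.9/7.8/3.4% | 5.2–9.2% | 2.8–6.4% |

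A wider pattern, 5/1.5/10/3%, gives 2.6–5.6% and 0.7–2.7%. So omitting unit type lowers the error as types diverge.

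**4. Site clustering kept, few clusters corrected.** With a G/(G−1) variance factor and t on G−1 df, the error is about 0.5–3.1%. Power at 5% v 3.5% is only about 11–35% (3 sites) or 14–49% (4 hospitals).

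**5. Clustering on the 14 units.**

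| Analysis | Type I error at RR 1.15 |
|---|---|
| Unit type in model, no correction, 1.96 | 7.6–8.4% |
| No unit type, Kauermann–Carroll, t on 12 df | 0.1–2.9% |
| Unit type, Kauermann–Carroll, t on 9 df | 2.5–2.9% |
| Permutation within strata, null at RR 1.15 | 2.0–3.0% |

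The 9 df are 14 units minus 5 mean parameters (arm and four unit types). Leaving unit type out also costs power: with the correction and t on 12 df, it falls from 66.9/60.0/30.6% with equal rates to 27.5/25.1/18.1% with the largest differences in step 3 (ICC 0/0.001/0.01).

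**6. Power of the corrected, stratum-adjusted test at about 1280 per group.** 61–63%, 54–56% and 28–29% at ICC 0, 0.001 and 0.01. As a check, the design effects are 1, 1 + 182 × 0.001 = 1.18 and 1 + 182 × 0.01 = 2.82, and noncentral t on 9 df gives 64%, 57% and 28%.

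**The case against.** The strongest replies are these.

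- **Units nest within sites, so site clustering already covers unit-level correlation.** This is correct. A reader might infer that the plan ignores within-unit correlation; it does not. The inflation comes from having 3 or 4 clusters with a normal reference.
- **Omitting unit type does not inflate the error.** Also correct. It lowers the error, so it should not be read as a second cause of false non-inferiority. It is a separate flaw: it makes the error rate depend on an unknown quantity and loses power.
- **The plan never says uncorrected or 1.96.** True. The inflated figures apply only if the usual sandwich is used. With a correction at site level the error is controlled, and the difficulty becomes power (step 4). The silence still leaves the primary test undefined.
- **Site may have been meant loosely as unit.** Aim 1A is analysed at unit level, so this is possible, but the sentence in section 6.2 that separates the two makes it unlikely. On that reading the uncorrected error without unit type is 0.4–5.3%, which is still not a controlled 2.5%.
- **Part of the power shortfall has another source.** This stands. At ICC 0, about 6 points come from the risk-difference scale of the sample-size method; the remaining 11–13 come from having few clusters.

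**Conclusion.** The concern holds, and nothing elsewhere in the protocol resolves it. With the usual uncorrected sandwich and 1.96, the one-sided error is about 13–14% (3 sites) or 10–12% (4 hospitals) if contamination is equal across unit types. That is roughly five or four times the nominal 2.5%. Under assumed type differences it falls to about 5–9% or 3–6%, and stronger differences can make it nominal or conservative. A reader might take the simulated figures as bounds, or conclude that the test must be anti-conservative. The documents support neither, because they give no unit-type rates and no ICC for Aim 1B.

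What does not depend on those values is narrower: no reading of site clustering delivers the stated 2.5% test with 80% power. Confidence is high in the defect, and conditional on the assumptions for its exact size.

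**What to change.** **Section 6.1, Aim 1B.** Replace the reference to clustering within site with a log-link GEE, independence working correlation, clustered on the 14 randomised units, with unit type in the model. Name a small-sample method: for example a Kauermann–Carroll corrected sandwich with t on 9 df, or a permutation test within strata with the null shifted to RR 1.15. The stratum terms and the correction are needed together (step 5). State that the one-sided p-value and the confidence limit for the relative risk both come from this one analysis.

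**Section 6.2, Aim 1B.** State an assumed ICC with its basis, and restate the power of 1280 per group for this test on the relative-risk scale: about 62%, 55% and 28% at assumed ICC 0, 0.001 and 0.01. The scale of the sample-size method can be handled as its own point.

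**Cost.** The change is to wording. Unit and unit type follow from the location already recorded with each sample (section 3, Aim 1B), so no extra data or enrolment is needed to make it. The price is wider intervals and a less favourable stated power. Whether that power is acceptable at the planned size is then a separate decision for the sponsor.

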6.2 Sample Size Estimates

Aim 1A:

How many participants (or specimens, or charts) will be used in this study?

UMMC: 6 units Worldwide: 14 units

14 units will be randomized to intervention or usual care. Over the 12-month study period we expect a minimum of 7000 total observations (14 units across the systems x 500 observations). Each system will have a research coordinator perform observations 3 hours per day four days per week. We estimate an average of 5 observations per hour¹⁹ (15 per day and 60 per week) and thus over 2500 observations per year per research coordinator are feasible (we expect to require fewer to achieve desired power). Average HH compliance is consistently at 40-50% and are often lower when glove use is indicated^{1,15}, we believe the compliance with infection prevention practices (i.e. primary outcome, composite compliance with HH AND glove use) in the usual care group will be ~40%. Recent studies have shown compliance with gloves when indicated to be approximately 70-80%¹⁵. Thus for the primary outcome, we expect a difference in compliance with infection prevention practice to be ~ 30%. If we assume 500 observations per area, an alpha level of 0.05, an interclass coefficient of 0.001²² we will require inclusion of 4 patient care areas (2 experimental and

2 usual care) to achieve a power greater than 90% power to detect an effect size of 30% (i.e. the primary outcome). If we vary the interclass coefficient to 0.01, we still have greater than 90% power under the same conditions. Relative to the secondary outcome, in which we will compare compliance with gloving only in both the direct gloving (i.e. experimental group) and the usual care group, we believe it is reasonable to expect that removing the cumbersome and time-consuming requirement of HH prior to glove use may increase compliance with glove use when indicated by approximately 10%. Using the same assumptions as the primary aim with an interclass coefficient of 0.001, we need to recruit and randomize 4 participating units to achieve > 90% power to detect this effect size of 10%. If we use the higher interclass coefficient of 0.01, we need 8 participating units to achieve > 85% power. So in short, we have ample power to see an effect in both primary and secondary outcomes including the sub-populations of adult ICU, dialysis and emergency department.

Aim 1B:

How many participants (or specimens, or charts) will be used in this study?

Local: 866 Worldwide: 2600

Based on pilot data, we anticipate 5% of HCWs in the usual care group (hand-hygiene plus gloves) and 3.5% in the experimental group (direct gloving) to have > 30 CFUs. We define non-inferiority as a relative risk < 1.15 of having > 30 CFUs, comparing the experimental group to the usual care group. That is, delta equal to 1.15. Under these assumptions, 1280 samples (per group) are sufficient for a one-sided test with alpha=0.025 to have 80% power to detect noninferiority.²³ 1280 samples in both groups will result in a total of 2560 samples for the 12-month study period. Spread across the 14 proposed participating units at the 3 healthcare systems (UMMC and STC will share a Research Associate), this is approximately 850 samples per site and 180 samples per participating unit over the 12-month study period. Thus, each site will need to recruit just over 70 HCWs each month to meet the goal sample size. In the pilot study 230 HCWs were recruited and agreed to participate in a single month.

7 Data Collection, Handling and Storage

All data collected will be stored in a relational database in order to digitize the data for analysis. No PHI will be collected. The database will be stored on a shared drive. Data from University of Iowa and Johns Hopkins Hospital will be sent electronically the investigators at the University of Maryland – data from Aim 1A is aggregate unit level data and not-human subjects data; and data from Aim 1B is completely de-identified.

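### Aim 1A: the stated power for 4 and 8 units ignores the few degrees of freedom between units, and the sub-population power claim is unsupported for glove use and for dialysis; the 14-unit comparison is adequate

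*Combined protocol and SAP*

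**What the plan says.** Section 6.2 (Aim 1A) sets its inputs as "If we assume 500 observations per area", "an alpha level of 0.05" and "an interclass coefficient of 0.001", with 0.01 as the higher value. It does not say whether alpha is one- or two-sided and names no reference distribution. Composite compliance "in the usual care group will be ~40" percent, with an expected difference of about 30 points. Glove compliance is put at about 70-80%, with a hoped-for gain of about 10 points.

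Four power statements follow:

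- Primary, 4 units (2 per arm), ICC 0.001: above 90%.
- Primary, 4 units, ICC 0.01: "If we vary the interclass coefficient to 0.01, we still have greater than 90% power under the same conditions".
- Glove use, ICC 0.001: "we need to recruit and randomize 4 participating units to achieve > 90% power to detect this effect size of 10" percent.
- Glove use, ICC 0.01: "we need 8 participating units to achieve > 85% power".

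The paragraph concludes that "we have ample power to see an effect in both primary and secondary outcomes including the sub-populations of adult ICU, dialysis and emergency department". It gives no power for the 14 units that will be randomised. Section 6.1 plans GEE for Aim 1A, with analysis at unit level, and names no small-sample correction.

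**The concern.** Treatment is assigned to units, so evidence about the treatment difference comes from variation between units. With two units per arm, that variation is estimated on 2 degrees of freedom and the two-sided 5% critical value is 4.30, not 1.96. With four per arm it is 2.45 on 6 degrees of freedom. A power figure computed with 1.96 is not power at the 5% level in a comparison this small: with that cutoff, a unit-level statistic would reject a true null about 19% of the time with 4 units and 10% with 8.

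What is at stake is how results by unit type are read. The 4- and 8-unit figures are the only support offered for the sub-population claim, and the sub-populations contain 3 or 4 units. A null result in dialysis or emergency units could be taken as evidence of no effect when the comparison had little chance of showing one.

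**Working it through.** **Inputs.** From Section 6.2: m = 500 observations per unit; ICC 0.001 or 0.01; primary 40 vs 70%; glove use 70 vs 80% as base case (70% fits the 30-point primary difference), with 75 vs 85 and 80 vs 90 as the range. Assumed: two-sided alpha 0.05 and equal arms where the number of units is even.

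**Formulas.** With k units per arm:

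- DEFF = 1 + 499 × ICC, which is 1.499 at ICC 0.001 and 5.99 at ICC 0.01.
- SE = √{[p0(1−p0) + p1(1−p1)] × DEFF / (500k)}; λ = (p1 − p0)/SE.
- Normal reference: power = Φ(λ − 1.96).
- t reference: power = P(T > t crit), with T noncentral t on 2k − 2 degrees of freedom and noncentrality λ.

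**Reproducing the plan's figures, then changing only the reference.**

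- Primary, 4 units, ICC 0.001: SE = √(0.45 × 1.499/1000) = 0.0260; λ = 11.55.
- Primary, 4 units, ICC 0.01: SE = √(0.45 × 5.99/1000) = 0.0519; λ = 5.78.
- Glove use 70 vs 80, 4 units, ICC 0.001: SE = √(0.37 × 1.499/1000) = 0.0236; λ = 4.25.
- Glove use 70 vs 80, 8 units, ICC 0.01: SE = √(0.37 × 5.99/2000) = 0.0333; λ = 3.00.

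| Case | Stated | Normal | t (df) |
|---|---|---|---|
| Primary, 4 units, ICC 0.001 | > 90% | > 99.9% | 99.9% (2) |
| Primary, 4 units, ICC 0.01 | > 90% | 99.99% | 81% (2) |
| Glove use, 4 units, ICC 0.001 | > 90% | 98.9% | 61% (2) |
| Glove use, 8 units, ICC 0.01 | > 85% | 85.2% | 71% (6) |

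The normal column satisfies all four statements, and 85.2% sits just above the stated 85%. A simulation of beta-binomial units with a unit-level t test gave 99.8%, 81.1%, 60.6% and 70.8% for the four rows.

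**Range over the glove baseline (t reference).**

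- 4 units, ICC 0.001: 61% (70 vs 80), 66% (75 vs 85), 74% (80 vs 90).
- 8 units, ICC 0.01: 71%, 77%, 86%.

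No baseline in the range satisfies both glove statements under a two-sided t reference, which supports the inference that a normal reference was used.

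**All 14 units.** Glove use 70 vs 80, ICC 0.01: SE = √(0.37 × 5.99/3500) = 0.0252; λ = 3.97; 12 degrees of freedom; power 95% (94% on 9 degrees of freedom if the four strata are fitted). The primary exceeds 99.9%.

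**Sub-populations.** By Section 3 there are 4 adult ICUs, 4 emergency-type units (including the Trauma Resuscitation Unit) and 3 dialysis units.

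- Four units, ICC 0.01, glove use 70 vs 80: SE = √(0.37 × 5.99/1000) = 0.0471; λ = 2.12. Power is 24% on 2 degrees of freedom, and only 57% with the normal reference.
- Three dialysis units must split 2:1, leaving 1 degree of freedom (critical value 12.71). Here SE = √{(DEFF/500) × [p0(1−p0)/k0 + p1(1−p1)/k1]}. At ICC 0.01, power is about 29% for the primary and 11% for glove use 70 vs 80. At ICC 0.001 it is about 54-55% for the primary and 21-27% for glove use, over both splits and the 70-80% baselines.

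**The case against.** The strongest reply is that the trial randomises 14 units, not 4 or 8, so the small figures are minimum requirements that the design comfortably exceeds. For the main comparison this stands. A reader might infer that the trial is underpowered or needs more units; the plan's own inputs do not support that.

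A reader might also infer a slip in arithmetic. There is none: every stated figure reproduces. The issue is the reference distribution, and that is inferred, because the plan does not name it.

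Sidedness matters. At one-sided 0.05 the primary with 4 units at ICC 0.01 reaches 96%, so that shortfall disappears. At 70 vs 80 the two glove figures would be about 84% each, still short. At 80 vs 90 the same formula gives about 93% (4 units) and 94% (8 units), so both would be met. But Section 6.2 mentions no one-sided test for Aim 1A, whereas it does so explicitly for Aim 1B.

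It would be too strong to say that every small-sample figure fails. The primary with 4 units at ICC 0.001 holds, and the 8-unit glove figure is met at 80 vs 90. Nor does the sub-population claim fail everywhere: for the primary, four adult ICUs or four emergency-type units give 99.9% at ICC 0.001 and 81% at ICC 0.01.

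Finally, the t figures describe an unadjusted unit-level test. The plan selects units with similar baseline compliance, stratifies and adjusts for covariates, which may gain precision or cost degrees of freedom. The figures are therefore approximations to the planned analysis.

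**Conclusion.** The point holds in a limited form. Under a two-sided 5% test at unit level, the 4-unit glove figure falls short across the whole baseline range, by at least 16 points (90 − 74). The 4-unit primary figure at ICC 0.01 falls short by about 9 points (90 − 81). The 8-unit glove figure is met only at the top of the baseline range.

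The sub-population claim is unsupported for glove use and for dialysis. For glove use at ICC 0.01 this does not depend on the choice of reference: the plan itself asks for 8 units, no sub-population has more than 4, and the normal method gives 57% at 70 vs 80.

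These conclusions rest on two-sided alpha, 500 observations in every unit, the plan's two ICC values and no covariate adjustment. On the same inputs the 14-unit comparison is adequate for both outcomes.

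**What to change.** In Section 6.2 (Aim 1A):

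1. State the sidedness of alpha, the glove baseline and the reference distribution.
2. Restate the small-sample figures on a t reference. For two-sided 0.05 and glove use 70 vs 80: at ICC 0.001, 61% with 4 units; at ICC 0.01, 71% with 8 units, 84% with 10, 91% with 12 and 95% with 14. For the primary with 4 units: 99.9% at ICC 0.001 and 81% at ICC 0.01.
3. Base the power claim on the 14 units that are randomised.
4. Replace the closing sub-population claim with a statement that results by unit type are descriptive, since Section 6.1 defines no such analysis for Aim 1A.

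The cost is wording, and some stated figures become less favourable. No extra units or observations are needed.
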